#### **16.1.1 Missing and Partial AE Onset Date/Time**

In the event that only a partial end date (month/year) is available, and month/year occurs before that of the first study drug administration date, the adverse event will be considered as non-treatment emergent. However, if the onset date is a partial date (month/year) and month/year occurs on or after that of study drug administration date, the following cases will be considered:

- If month/year of the onset date is greater than the month/year of study drug administration date, the adverse event will be considered treatment-emergent.
- If month/year of the onset date is equal to the month/year of study drug administration date, and the end date is present, the end date will be used to determine if the adverse event is treatment emergent. If the end date is on or after study drug administration date, the adverse event will be considered treatment-emergent; otherwise, if the adverse event stopped before study drug administration date, then it will not be treatment-emergent;
- If month/year of the onset date is equal to the month/year of study drug administration date, and the end date is a partial date, the adverse event will be considered treatment emergent.
- If adverse event onset date is known and time is missing then the time will be considered as post dose.

## **16.2 Vital Signs**

Descriptive summaries of actual values and changes from pre-dose to 10 min, 60 min (1 hr), 120 min, 240 min (4 hr), and 720 minutes (12 hr) post-dose will be calculated for heart rate, systolic blood pressure, and diastolic blood pressure and presented by treatment group.

## **16.3 ECG**

Descriptive summaries of actual values and changes from pre-dose by treatment group will also be provided for the quantitative ECG parameters of rhythm, heart rate, PR interval, QRS interval, QT, QTcF, (Fridericia's) corrections for heart rate.

## **16.4 Investigator Skin Assessments**

Scores of the investigator skin assessments of the application sites at 30 min (30 min wear time assignment only), 60 min (1 hr), 12 hours and 24 hours post-dose will be summarized by treatment group using frequency tables.

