### **7.3.4 Investigator Visual Skin Assessments of the Application Sites**

Each M207 patch site (where a patch has been removed) will be observed for the following skin assessments pre-dose and immediately after removal of the patches from the subject's skin (and before swabbing) at 30 min (for 30 min wear time treatment groups only), 60 min, 12 hr, 24 hr and at the End of Study/or Early Termination visit.

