## **3.0 Study Objectives**

1. To compare the pharmacokinetics, safety and tolerability of M207 3.8 mg administered to either the upper arm or thigh, particularly with respect to skin irritation (erythema, edema, bruising, bleeding)
2. To compare the pharmacokinetics, safety and tolerability of M207 3.8 mg worn for either 30 minutes or 1 hour on the upper arm
3. To compare the pharmacokinetics, safety and tolerability of M207 3.8 mg to intranasal zolmitriptan 2.5 mg

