## **4.0 Study Description**

### **4.1 Randomization and Blinding**

The 24 subjects are planned to receive each of the four treatments (A, B, C, D) 48 hours apart.

The order of receiving of the investigational products for each subject will be determined according to a randomization schedule which will be appropriate to the study design. Subjects will be randomized to one of the four sequences: either ABCD or BDAC or CADB or DCBA. Equal allocation of the sequence will be ensured.

The randomization schedule will be generated using SAS® statistical software (Version: 9.4; SAS Institute Inc, USA), by a biostatistician of Clianza Research Limited. The randomization schedule will be maintained under controlled access.

The personnel involved in the dispensing of investigational products will be accountable for ensuring compliance to randomization schedule.

At the end of each dosing day, the safety data from the subjects will be evaluated. If tolerability is deemed to be acceptable by the Principal Investigator, a decision will be made to proceed to the next dosing day.

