## 4.5 Study Design, Treatment and Plan

This is a single-center, open-label, randomized, four-way crossover study. Each subject will receive each of the four study treatments once, followed by in-clinic monitoring and extensive blood sample collection for pharmacokinetic analysis.

Dosing will occur approximately 48 hours apart, until completion of dosing in randomized order per the treatment sequence tables. Plasma samples from the dosing days will be sent to the analytical laboratory for analysis and tolerability for each of the dose levels will be summarized.

After completion of the four dosing days, subjects will be assessed one final time and dismissed from the study.

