**Formula for calculation of Frel;**

**Frel = 100\*(AUCx\*Dy) / (AUCy\*Dx);** where relative bioavailability measures the bioavailability (estimated as the AUC) of a treatment-X when compared with treatment-Y of the same drug. **D** is the dose administered.

Frel will be calculated for AUCt.

Ratios will be reported for AUC(0-30mins), AUC(0-60mins), AUC(0-120mins), AUCt, AUCi and Cmax.

No value of Kel, AUCi or tHalf will be reported for cases that do not exhibit a terminal log-linear phase in the concentration versus time profile.

- *Descriptive statistics:* Mean, standard deviation, coefficient of variance, Median, Maximum and Minimum for applicable pharmacokinetic parameters will be calculated.

- *Statistical analysis:* Statistical analysis will be performed on pharmacokinetic data of subjects using SAS® statistical software (Version: 9.4 or higher; SAS Institute Inc, USA).
- *Analysis of Variance:* Ln-transformed data of Cmax, AUC(0-30mins), AUC(0-60mins), AUC(0-120mins), AUCt and AUCi will be evaluated statistically using the PROC MIXED procedure from SAS® for difference due to treatment, with period and sequence as a fixed effects and subject within sequence as a random effect.

All main effects will be tested at 5% level of significance using the Mean Square Error as the error term.

- Two one-sided 90% confidence intervals for the ratio of means between drug formulations will be calculated for Ln-transformed data of Cmax, AUC(0-30mins), AUC(0-60mins), AUC(0-120mins), AUCt and AUCi.

The data of metabolite n-desmethyl zolmitriptan will be provided as supportive information.

The comparisons of interest will be treatment A vs. B, A vs. C, A vs. D, B vs. C, B vs. D and C vs. D.

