**Summary Table 14.3.6: Frequency by Treatment for Investigator Visual Skin Evaluation**

Frequency_Erythema							
Variables		Pre-dose	30 minutes	60 minutes	12 hour	24 hour	48 hour
Treatment (A) - M207 Arm 30 minutes	0						
	1						
	2						
	3						

Note: Same tables needs to be followed for rest of the treatments and variables i.e. Edema, Bruising and Bleeding.

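### Objective 1 singles out skin irritation for upper arm versus thigh, but the SAP specifies only separate per-treatment summaries of skin scores and no within-subject comparison

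*SAP*

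**What the plan says.** SAP 3.0 sets Objective 1 as a comparison of upper arm and thigh, "particularly with respect to skin irritation (erythema, edema, bruising, bleeding"). No other outcome is singled out in this way. Objective 2 compares 30-minute with 1-hour wear on the upper arm. SAP 4.5 describes the design: "Each subject will receive each of the four study treatments once".

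SAP 16.4 plans that skin scores at patch removal, "12 hours and 24 hours post-dose will be summarized by treatment group using frequency tables". Protocol 10.5 says the same. Two shells implement this. Table 14.3.5 gives N, mean, SD, minimum, maximum and median by treatment and time point. Table 14.3.6, "Frequency by Treatment for Investigator Visual Skin Evaluation", gives counts of scores 0 to 3. Listing 16.2.8.8 shows individual scores by subject and patch site.

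Other outcomes are treated differently. SAP 11.0 fits a mixed model to the PK parameters with subject as a random effect, and states: "The comparisons of interest will be treatment A vs. B, A vs. C, A vs. D", followed by the remaining three pairs. SAP 18.0 says that mean adhesion scores will be compared between test products.

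SAP 7.0 prescribes LOCF for missing skin scores. The worked example in SAP 12.0 says that the filled scores are for statistical analysis.

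On the unit of scoring, Protocol 7.3.4 says: "Each M207 patch site (where a patch has been removed) will be observed for the following skin assessments". Each M207 dose uses two patches.

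**The concern.** A crossover removes stable differences between people from a treatment comparison. Here those include how readily a person's skin reddens or bruises and how visible that is to the assessor. The benefit is obtained only if the analysis compares treatments within subjects. Two frequency columns placed side by side do not do this, because the same columns are compatible with many pairings.

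The report could therefore describe irritation on the arm and on the thigh separately without giving a planned estimate of the difference, or its uncertainty, for the outcome that Objective 1 emphasizes. If the comparison is made later, someone must then choose the cut-off, the time point and the way to combine two patch sites after seeing open-label scores.

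The undefined unit adds ambiguity. A count in Table 14.3.6 could be out of 24 subjects or 48 sites, and two sites on one subject are not independent observations.

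**Working it through.** **What is specified for each outcome**

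| Outcome | Per-treatment summary | Comparison between treatments |
|---|---|---|
| PK (SAP 11.0, Table 14.2.2.1) | Yes | Six pairs, ratios with 90% intervals |
| Adhesion (SAP 18.0) | Yes | Means to be compared |
| Skin scores (SAP 16.4, Tables 14.3.5 and 14.3.6) | Yes | None |

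The LOCF example in SAP 12.0 refers to a statistical analysis of skin scores, but none is defined. That suggests an omission rather than a settled choice.

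**There is no plan figure to reproduce.** SAP 4.4 gives no sample size calculation, and neither document gives a rate, SD or correlation for skin scores. Everything below except n = 24 is assumed.

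**Same frequency table, different pairings.** Suppose 14 of 24 subjects score 2 or more on the arm and 7 of 24 on the thigh. The difference is 7/24 = 29 points. Let b be the number of subjects with the event on the arm only and c on the thigh only, so b − c = 7.

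- Within-subject correlation: phi = (both × neither − b × c) / √(14 × 10 × 7 × 17), with denominator √16660 = 129.1.
- Standard error of the paired difference: √[(b + c) − (b − c)²/24] / 24.
- Exact McNemar p: two-sided binomial on b + c discordant pairs.

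| Both | b | c | Neither | phi | SE | 95% Wald interval (points) | Exact p |
|---|---|---|---|---|---|---|---|
| 7 | 7 | 0 | 10 | 70/129.1 = 0.54 | √4.958/24 = 0.093 | 11 to 47 | 2/128 = 0.016 |
| 6 | 8 | 1 | 9 | (54 − 8)/129.1 = 0.36 | √6.958/24 = 0.110 | 8 to 51 | 20/512 = 0.039 |

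Reading the same columns as if they came from unrelated groups gives SE = √[(0.583 × 0.417 + 0.292 × 0.708)/24] = 0.137 and an interval of 2 to 56 points.

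**Gain in precision from pairing.** For assumed proportions of 0.5 and 0.3, the unpaired variance per subject is 0.25 + 0.21 = 0.46. The paired variance is 0.46 − 2 × phi × √(0.25 × 0.21) = 0.46 − 0.458 × phi. These margins limit phi to (0.30 − 0.15)/0.229 = 0.65.

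| phi | Paired variance | SE ratio, paired to unpaired | Interval narrower by |
|---|---|---|---|
| 0.3 | 0.323 | 0.84 | 16% |
| 0.5 | 0.231 | 0.71 | 29% |
| 0.65 (maximum) | 0.160 | 0.59 | 41% |

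**Period and carry-over.** SAP 4.1 states: "Subjects will be randomized to one of the four sequences: either ABCD or BDAC or CADB or DCBA". Each treatment occurs once in each period, so with equal allocation and complete data an additive period effect cancels from a simple paired difference. A and C, both on the upper arm, fall in consecutive periods in two sequences (BDAC and CADB). At 24/4 = 6 subjects per sequence, that is 12 of 24 subjects with upper-arm doses about 48 hours apart.

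**The case against.** The strongest defence is that descriptive reporting matches the stated aim. SAP 4.4 and Protocol 10.1 say that 24 subjects were enough in earlier studies for directional information on tolerability, and no formal calculation was done. Adverse events, vital signs and ECG are also summarized by treatment without contrasts. This stands: descriptive skin tables are not an error in a Phase 1 study, and no powered test is called for. But direction within a subject is what separate columns leave unclear, and skin irritation, unlike vital signs or ECG, is the outcome that Objective 1 names.

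A second defence is that nothing is lost. Listing 16.2.8.8 keeps subject and site, and the introduction to the mock tables allows tables to be added or modified. This also stands, and it limits the point to prespecification.

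A reader might infer more than the documents support:

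- That skin scores get frequency counts and nothing else. Table 14.3.5 and Listing 16.2.8.8 go further.
- That the pairing could decide whether a difference looks convincing. With the margins above, 14 vs 7 discordant pairs would give p = 0.189. But that requires no subject to react at both locations (phi = −98/129.1 = −0.76), which is implausible for reactions of the same person's skin.
- That counting 48 sites makes a planned standard error too small. The SAP plans no standard error, interval or test for skin scores, so the 24-or-48 question is one of labelling and definition.

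**Conclusion.** The point holds as a cheap improvement, of minor to moderate severity. Neither document specifies a within-subject comparison of skin scores for A vs B or A vs C, although the objectives ask for comparisons and the design supplies paired data. The shells also leave the unit of N undefined.

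It would go too far to say that the trial cannot compare irritation between arm and thigh. The scores are collected and listed by subject and site, so the comparison remains possible; it is not planned.

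The size depends on a within-subject correlation that the documents do not give. For assumed proportions of 0.5 and 0.3, pairing narrows the interval by 16% to 41% over correlations from 0.3 to the attainable maximum of 0.65. If reactions at arm and thigh are nearly unrelated within a person, the gain in precision is small. Defining the comparison and the unit in advance is still worthwhile in that case.

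**What to change.** Add a paragraph to SAP 16.4:

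- **Unit.** For each subject, treatment, sign and time point, take the worse of the two patch-site scores. State that N counts subjects in Tables 14.3.5 and 14.3.6. Keep both sites in the listing.
- **Comparisons.** A vs B is the main one, for Objective 1; A vs C serves Objective 2.
- **Main display.** For each of the four signs at patch removal, give the within-subject cross-tabulation of scores and the paired difference in the percentage of subjects scoring 2 or more, with a 95% interval for paired proportions.
- **Supportive displays.** Repeat for 12 h, 24 h and the cut-off of 1 or more. The later times matter for A vs C because removal falls at 30 minutes for A and 60 minutes for C.
- **Pre-dose scores.** Show them alongside, because doses are about 48 hours apart and A and C share the upper arm.
- **Missing scores.** Use observed scores in the main table and LOCF as supportive. This also defines the analysis that SAP 12.0 mentions.
- **Status.** State that all results are descriptive and unadjusted.

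Ranking the displays matters. Four signs × three times × two cut-offs × two comparisons make 48 differences; the main display holds 4 × 2 = 8, of which four address Objective 1.

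The cost is SAP wording and two extra tables, with no new data. The downside is several unadjusted intervals in 24 subjects, which should not be read as formal tests.

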## **16.5 Clinical Laboratory Evaluations**

Clinical laboratory values will be displayed in data listings, including a listing of all abnormal results. Clinically significant values will be flagged.

## **16.6 Physical examination**

Results of physical examinations conducted throughout the study will be presented in data listings, including abnormalities.

## **17.0 Medical history**

Medical history data will be presented in listings.

## **18.0 Patch Adhesion**

Adhesion scores will be summarized by time point and treatment group using frequency tables. Mean adhesion scored by time point and treatment group will also be provided. The means of the per treatment group mean adhesion score for the different test products will be compared.

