### **6.3.1.8 30 Minutes after Treatment Administration**

- Collect blood for a PK sample
- Record concomitant medications and adverse events
- Record patch adhesion score
- Remove patches and perform the following procedures in the order listed below (for 30 minute wear time treatment assignment only):

- Investigator visual skin assessment of the patch application sites
- Retain and package patches for freezing. Refer to full instructions in [Appendix 3](#).
- Application site swabbing. Refer to full instructions in [Appendix 3](#).

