#### **6.3.1.10 60 Minutes after Treatment Administration**

- Collect blood for a PK sample
- Measure vital signs
- Record a 12-lead ECG
- Record concomitant medications and adverse events
- Record patch adhesion score (60 minute wear time assignment only)
- Remove patches and perform the following procedures in the order listed below (for 60 min wear time assignment only):
  - Investigator visual skin assessment of the application sites
  - Retain and package patches for freezing. Refer to full instructions in [Appendix 3](#).
  - Application site swabbing. Refer to full instructions in [Appendix 3](#).

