### 13 SCHEDULE OF ASSESSMENTS

Assessment*	Screening Visit**	Admission/ baseline	Dosing Visit***																End of Study/Early Termination	
			Pre-dose	0 mn	2 mn	5 mn	10 mn	15 mn	20 mn	30 mn	45 mn	60 mn	90 mn	2 hr	4 hr	8 hr	12 hr	24 hr		
	Screening	Day Prior to Each Dose																	Within 48 hours after completion of all procedures on final dosing day	
Informed consent	X																			
Medical history/ demographics	X																			
Concomitant medications																			→	
Physical exam	X																X		X	
Serum pregnancy test	X																		X	
Urine dipstick pregnancy test		X																		
Height	X																			
Weight	X																		X	
Confirm eligibility	X	X	X																	
Clinical laboratory tests (CBC, hematology, UA)	X																		X	
Serology	X																			
Urine Drug & Alcohol (breath) Testing	X	X																		
Collect PK samples			X	X	X	X	X	X	X	X	X	X	X	X	X	X	X	X		
Study drug administration				X																
Patch Adhesion Scale ∞			X							X ∞		X ∞								
Vital signs	X		X				X					X		X	X		X		X	
ECG	X		X					X				X				X	X		X	

Assessment*	Screening Visit**	Admission/baseline	Dosing Visit***																End of Study/Early Termination
			Pre-dose	0 mn	2 mn	5 mn	10 mn	15 mn	20 mn	30 mn	45 mn	60 mn	90 mn	2 hr	4 hr	8 hr	12 hr	24 hr	
Remove and retain (freeze) patches (at 30 min or 60 min depending on assignment)	Screening	Day Prior to Each Dose								X		X							Within 48 hours after completion of all procedures on final dosing day
Investigator skin assessment of the application sites*			X							X•		X•				X	X	X	
Swabbing****										X		X							
Record Adverse events																			→

\* When multiple procedures are scheduled for the same time point, PK samples will be taken at the protocol assigned time point within plus or minus 1 minute of the specified time points for the first hour and within plus or minus 5 minutes of the specified time points after one hour. The other measurements (i.e., vital signs, ECG, skin assessments) will be taken before or after the protocol-specified time point within an interval of plus or minus 5 minutes.

\*\* Screening Visit – Up to 30 days prior to first admission/baseline visit.

\*\*\* The washout period following each dose must be a minimum of 48 hours until the next dose is administered.

◦ Patch Adhesion Scale – Only the 60 min wear time treatment assignment will have the scale completed at both 30 and 60 min.

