### **Adhesion Data:**

Actual Adhesion score presented in below Table;

Subject	Adhesion scoring_Time Points(Hrs)		
	0.0	30 minutes	60 minutes
1	0	0	0
2	0	2	2
3	0	1	1

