**Listing 3: Listing of Adhesion Score for Test Treatment (C) - M207 Arm 60 minutes**

Subject No.	Sequence	Pre-Dose	30 minutes	60 minutes	Mean Score
XXXX					
XXXX					
XXXX					

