**Summary Table 14.3.2: Descriptive Statistics by Treatment for Adhesion**

Variable	N	Mean	Std Dev	Minimum	Maximum	Median
Treatment (A) - M207 Arm 30 minutes						
Treatment (B) - M207 Thigh 30 minutes						
Treatment (C) - M207 Arm 60 minutes						

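### The SAP compares one mean adhesion score per treatment without a common time window, although treatment C is scored at one more time point than A and B

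*SAP*

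**What the plan says.** Adhesion is scored from 0 (at least 90% adhered) to 4 (detached) and is listed among the safety and tolerability endpoints (Protocol 4.2, SAP 5.1).

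- **When it is scored.** Protocol 6.3.1.2 has a score at application and 6.3.1.8 one at 30 minutes, both for all patch treatments. Section 6.3.1.10 limits the 60-minute score to the 60-minute wear assignment. The footnote in Protocol section 13 agrees: "Only the 60 min wear time treatment assignment will have the scale completed at both 30 and 60 min".
- **What is summarised.** SAP 18.0 plans frequency tables by time point and treatment, and adds: "Mean adhesion scored by time point and treatment group will also be provided".
- **What is compared.** The next sentence of SAP 18.0 reads: "The means of the per treatment group mean adhesion score for the different test products will be compared". It gives no time window, time point or test.
- **Shells.** Summary Tables 14.3.2 and 14.3.7 share the title "Descriptive Statistics by Treatment for Adhesion". Each has one row per treatment and no time-point dimension. Listings 3 and 14.2.14, for C, show three scores followed by a Mean Score column. The matching listings for A and B (1, 2, 14.2.12 and 14.2.13) show two scores and no mean column.

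Protocol 10.6 leaves further detail on the adhesion analysis to the SAP, so the SAP is where the window should be defined.

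**The concern.** A single score per treatment is compared across treatments that were scored at different sets of times. A mean over two times and a mean over three times are different quantities. They can differ even when the patches adhered equally well at every time they were scored.

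The application score adds to this. Appendix 1 tells staff to press down lifted or curled edges right after application, so a low first score is plausible. That score has weight one half in a two-point mean and one third in a three-point mean.

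The comparison at stake is 30 minutes against 1 hour of wear on the upper arm, which is the study's second objective. Adhesion is one of the endpoints bearing on tolerability in that contrast.

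**Working it through.** The documents give no planned or expected mean adhesion score, so there is no figure to reproduce. The check applies each plausible averaging window to the same scores and asks whether A or B and C then agree.

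**Inputs.** SAP 12.0, under Adhesion Data, gives illustrative scores for three subjects at 0, 30 and 60 minutes: (0, 0, 0), (0, 2, 2) and (0, 1, 1). Every treatment is given this same profile. A and B use the scores at 0 and 30 minutes; C uses all three.

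**Subject values**
- Mean over 0 and 30: 0, (0+2)/2 = 1, (0+1)/2 = 0.5. Group mean 1.5/3 = 0.50.
- Mean over 0, 30 and 60: 0, 4/3 = 1.33, 2/3 = 0.67. Group mean 2/3 = 0.67.
- 30-minute score alone: 0, 2, 1. Group mean 3/3 = 1.00.
- Mean over 30 and 60: 0, 2, 1. Group mean 1.00.

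**Comparison under each reading**

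| Window for A, B | Window for C | A or B | C | C minus A or B |
|---|---|---|---|---|
| 0, 30 | 0, 30, 60 | 0.50 | 0.67 | +0.17 |
| 30 only | 0, 30, 60 | 1.00 | 0.67 | −0.33 |
| 30 only | 30, 60 | 1.00 | 1.00 | 0 |
| 0, 30 | 0, 30 | 0.50 | 0.50 | 0 |
| 30 only | 30 only | 1.00 | 1.00 | 0 |

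The third row agrees only because the example is flat from 30 to 60 minutes. With illustrative profiles (0, 0, 0), (0, 1, 2) and (0, 1, 2), A or B at 30 minutes averages 2/3 = 0.67. C over 30 and 60 averages (0 + 1.5 + 1.5)/3 = 1.00, although the 30-minute scores are the same.

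**General form of the first reading.** For scores a, b, c at 0, 30 and 60 minutes, the gap is

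(a+b+c)/3 − (a+b)/2 = (2c − a − b)/6.

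For a profile 0, s, s this is s/6: 0.17 at s = 1 and 0.67 at s = 4. The gap is zero only when c = (a+b)/2. If adhesion does not improve over time (a ≤ b ≤ c), that requires a = b = c. Of the 35 non-decreasing profiles on the 0 to 4 scale, 5 are constant and score equally; the other 30 do not.

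**A versus B.** Both have the same two time points, so any window applied alike to both gives comparable scores.

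**The case against.** The strongest reply is that the time-matched result is already planned. SAP 18.0 promises frequencies and means by time point and treatment, so the 30-minute scores of A, B and C will be reported. The SAP also allows mock tables to be added or modified. The comparison has no test, margin or decision rule, there was no formal sample-size calculation, and the objectives do not name adhesion. All of this stands and limits the consequence. It does not settle the matter, because the sentence that names a comparison uses the per-treatment mean, and both adhesion table shells omit time. The skin-score shells (14.3.5 and 14.3.6) do show time points.

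A reader might infer more: that the plan averages A and B over 0 and 30 minutes, so the 1-hour treatment will look about 33% worse. The documents do not support this.

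- Nothing states that A and B are averaged over 0 and 30 minutes; their listings have no mean column.
- The sign depends on that inference, and another reading reverses it.
- The 33% is algebra for any 0, s, s profile: (2s/3)/(s/2) = 1.33. The scores are a worked illustration, not data or a forecast.
- Identical adhesion does not always give different scores. Full adhesion throughout scores 0 in every treatment.

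Nor is a time-averaged score wrong in itself. The difficulty is comparing averages taken over different times.

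**Conclusion.** The concern holds as an undefined window, not as a bias of known direction. Following the SAP text and shells can mix a two-point or single-point score for A and B with a three-point mean for C, and so create a wear-time difference where none exists.

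On the SAP's illustrative scores the artefact is +0.17 or −0.33 on the 0 to 4 scale, depending on a choice left to programming. These sizes assume identical scores at the shared times and no change from 30 to 60 minutes. They say nothing about adhesion expected in this trial. If nearly all patches stay fully adhered, the artefact will be close to zero.

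Only comparisons with C are affected. Since the comparison is descriptive and by-time-point summaries are promised, this should be corrected before the SAP is final, but it does not threaten the study's main conclusions.

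**What to change.** Replace the comparison sentence in SAP 18.0 with text to this effect:

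> Adhesion of A, B and C will be compared on the 30-minute score, the post-application time common to all three. The 60-minute score for C will be reported separately. If scores at patch removal are shown (30 minutes for A and B, 60 minutes for C), the table will be labelled as comparing different wear times.

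Then:
- add a time-point dimension to Summary Tables 14.3.2 and 14.3.7;
- state that the three-point Mean Score in Listings 3 and 14.2.14 is not used in the between-treatment comparison, or drop the column.

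A mean over 0 and 30 minutes for all three treatments would also remove the artefact. The 30-minute score is preferable because the application score does not dilute it.

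The cost is a short SAP text change and edits to two table shells, with a note on or edit to two listing shells. The by-time-point summaries already planned use the same data, so no new data are needed.
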